7.0 Eligibility Screening

7.1 *Describe screening procedures for determining subjects’ eligibility.*

Screening refers to determining if prospective participants meet inclusion and exclusion criteria.

 *Include all relevant screening documents with your submission (e.g. screening protocol, script, questionnaire).*

Response:

The PI or research assistants will be responsible for screening potential participants. Participants will be asked a series of questions over the phone (see phone scripts and questionnaires for young adults and individuals with stroke). When participants arrive for their first scheduled session, they will complete a cognitive assessment (Mattis Dementia Rating Scale- Dementia Rating Scale-2™ (DRS-2™) <http://www4.parinc.com/Products/Product.aspx?ProductID=DRS-2>, this trademark assessment will be purchased for the study information on the

assessment is found at the given website), The Montreal Cognitive assessment may also be used. A movement screen (range of motion and proprioception) and assessments for spasticity (Modified Ashworth Scale) will also be conducted prior to starting the testing. If the individual demonstrates severe limitations in movement, they will not complete the testing session. They will be paid for coming to the testing session on South Campus.

- N/A:** There is no screening as part of this protocol.

8.0 Recruitment Methods

- N/A:** This is a records review only, and subjects will not be recruited. *NOTE: If you select this option, please make sure that all records review procedures and inclusion/exclusion screening are adequately described in other sections.*

8.1 *Describe when, where, and how potential subjects will be recruited.*

NOTE: Recruitment refers to how you are identifying potential participants and introducing them to the study. Include specific methods you will use (e.g. searching charts for specific ICD code numbers, Research Participant Groups, posted advertisements, etc.).

Response:

Recruitment strategies for young adults will consist of flyers posted on UB campuses. Recruitment for individuals with stroke will be extensive including distribution of flyers through organizations such as Meals on Wheels, the Program of All-Inclusive Care for the Elderly (PACE), stroke support groups, senior centers and clinical facilities in the greater Buffalo region. In addition, advertisements will be placed in local papers and flyers at community centers. Final versions of the newspaper advertisements will be submitted to as an amendment to the IRB for approval prior to the printed ad. We will also ask the Buffalo Research Registry for a list of potential participants to contact and determine if they are interested in participating and if they are a good fit.

8.2 *Describe how you will protect the privacy interests of prospective subjects during the recruitment process.*

NOTE: Privacy refers to an individual's right to control access to him or herself.

Response: Participants will self-select to respond to one of the advertisements for the study. They need to choose to contact the researchers to participate in the study. The settings for the phone conversation and data collection will be private areas.

8.3 *Identify any materials that will be used to recruit subjects.*

NOTE: Examples include scripts for telephone calls, in person announcements / presentations, email invitations.

0 For advertisements, include the final copy of printed advertisements with your submission. When advertisements are taped for broadcast, attach the final audio/video tape. NOTE: You may submit the wording of the advertisement prior to taping to ensure there will be no IRB-required revisions, provided the IRB also reviews and approves the final version.

Response:

Flyers, advertisements, and follow up phone conversations- see phone scripts will be used to recruit participants. The flyer will be used as the advertisements.

9.0 Procedures Involved

9.1 Provide a description of **all research procedures or activities** being performed and when they are performed once a subject is screened and determined to be eligible. Provide as much detail as possible.

NOTE: This should serve as a blueprint for your study and include enough detail so that another investigator could pick up your protocol and replicate the research. For studies that have multiple or complex visits or procedures, consider the addition of a schedule of events table in in your response.

Approach: Our goal is to develop portable technology capable of cueing a home training program, collecting data on upper limb motor performance and providing user feedback on performance.

Response: Aim 1: Participants will be asked to come to Kimball Tower three times within a two week time span to demonstrate consistency of motor performance. An infrared motion monitor system will be used to track their movement and compare kinematics produced by the smartphone with kinematics produced from the infrared motion monitor system. Participants may be video taped during data collection to further assess mobility.

Aim 2

Wolf Motor Function Test (WMFT): examines functional abilities. It is a valid and reliable outcome measure following stroke

9-Hole Peg Test: a timed test of manual dexterity which involves lifting/placing/removing 9 pegs into/out of holes. It is both valid and reliable in measuring arm function after stroke.

Grip assessment: Grip strength is measured with a hand dynamometer.

Berg Balance Scale: A 14-item scale designed to measure balance

All clinical assessments are recommended Outcome Measures by the APTA for stroke (<http://www.neuropt.org/professionalresources/neurology-section-outcome-measures-recommendations/stroke>)

Use of smartphone and 3D printed objects will be in home over a 11- week span. Five of these weeks the participants will perform a limited number of task trials without feedback to act as a probe for performance quality. The other 6 weeks, participants will be asked to perform their exercise program 5/7 days and the in home exercise program may take up to an hour to complete.

User Feedback Measures: User Interaction Satisfaction: We will ask participants to rate the effectiveness of the information displays in supporting a set of key needs. The Questionnaire for User Interaction Satisfaction (QUIS) is a validated usability assessment tool applied in numerous studies of interface design (80-82, information on online assessment found at <http://www.lap.umd.edu/QUIS/index.html>), including assessment of health information interfaces (83-85). This licensed, online questionnaire will be supplemented with context specific questions related to the display. Comments and Debriefing: Participant will be interviewed to obtain additional feedback on their overall experience during the test. A semi-structured interview will be used in which broad questions are formulated and the conversation progresses. Findings from these components will be used to make iterative improvements as necessary to the system to support future research and implementation

Caregiver Feedback Measures: Caregivers of participants will be given the opportunity to provide their feedback on mRehab and the participant's use of the mRehab system. A semi-structured interview will be used to gain feedback on how much assistance caregiver's provided for 1) setting up mRehab, 2) providing motivation to use mRehab, 3) assisting the participant in using mRehab and 4) suggestions for improving mRehab.

9.2 Describe what data will be collected.

NOTE: For studies with multiple data collection points or long-term follow up, consider the addition of a schedule or table in your response.

Response:

Aim 1:

The controlled environment will allow us to measure motion accuracy and thus calculate gold standard numbers for jerk score, task completion, total path length, and other qualitative metrics (i.e., the number of repetitions). Video assessments will allow us to review motor behavior and further assess mobility.

Aim 2:

Clinical Assessments used to determine mobility of the more affected limb:

Wolf Motor Function Test (WMFT): examines functional abilities. It is a valid and reliable outcome measure following stroke

9-Hole Peg Test: a timed test of manual dexterity which involves lifting/placing/removing 9 pegs into/out of holes. It is both valid and reliable in measuring arm function after stroke.

Grip assessment: Grip strength is measured with a hand dynamometer.

Modified Ashworth Scale: Assesses spasticity

Probes: Perform the ADLs from the training program without feedback.

Performance will be assessed by examining data collected from the smartphone:

Participants will be asked to complete only two repetitions of the training tasks without receiving feedback on three separate days during each baseline week and each follow-up week to determine baseline performance and in follow-up retention of task learning.

Performance Measures: We will examine the following measurements of movement and task performance for comparison between the baseline and training intervention periods:

Task completion time: Measured from the start to the end of the task.

Normalized jerk score (NJS)/smoothness: Using the acceleration readings from the inertial measurement unit embedded in the smartphone, the normalized jerk score can be computed.

Usability: Participants will evaluate the usability of the system based on ease of use and interpretability of the feedback. Usage metrics will be recorded to track how often and for how long they use the system at home. Also, a post-survey study will be used to collect quantitative participant feedback for UI improvement.

User Feedback Measures: User Interaction Satisfaction: We will ask participants to rate the effectiveness of the information displays in supporting a set of key needs. The Questionnaire for User Interaction Satisfaction (QUIS) is a validated usability assessment tool applied in numerous studies of interface design, including assessment of health information interface. This licensed, online questionnaire will be supplemented with context specific questions related to the display. Semistructured interviews will also be used.

Caregiver Feedback Measures: Caregivers will be given the option of participating in a semi-structured interview to assess their feedback on how much assistance the caregiver provided for 1) setting up mRehab, 2) providing motivation to use mRehab, 3) assisting the participant in using mRehab and 4) suggestions for improving mRehab.

9.3 List any instruments or measurement tools used to collect data (e.g. questionnaire, interview guide, validated instrument, data collection form).

 *Include copies of these documents with your submission.*

Response:

List of instruments used in study:

Questionnaires for young adults and adults with stroke

Mattis Dementia Rating Scale- Licensed manual with scoring software

<http://www4.parinc.com/Products/Product.aspx?ProductID=DRS-2>

Montreal Cognitive Assessment

Clinical Assessments:

Wolf Motor Function Test

9-hole peg test

Modified Ashworth Scale

Grip Strength- measured with hand dynamometer; *the hand dynamometer is an instrument used to measure the strength of the hand and forearm muscles by asking the participant to squeeze the dynamometer with as much force as possible.*

Berg Balance Scale

The Questionnaire for User Interaction Satisfaction (QUIS)- licensed online assessment , <http://www.lap.umd.edu/QUIS/index.html>

Semi-structured interview for participants

Semi-structured interview for caregivers

A modification will be submitted to upload the QUIS and Mattis Dementia Rating Scale after funding is received for the project and the license and the test is purchased.

9.4 *Describe any source records that will be used to collect data about subjects (e.g. school records, electronic medical records).*

Response: Not applicable

9.5 *Indicate whether or not **individual** subject results, such as results of investigational diagnostic tests, genetic tests, or incidental findings will be shared with subjects or others (e.g., the subject's primary care physician) and if so, describe how these will be shared.*

Response:

9.6 If participants ask about their performance, we could inform them of their performance on the clinical assessments. *Indicate whether or not study*

results will be shared with subjects or others, and if so, describe how these will be shared.

Response:

Data from the study will be analyzed and will be presented in professional journals and conferences.

10.0 Study Timelines

10.1 Describe the anticipated duration needed to enroll all study subjects.

Response:

It is anticipated that all participants will be enrolled within two years of the start of the study.

10.2 Describe the duration of an individual subject's participation in the study. Include length of study visits, and overall study follow-up time.

Response:

Aim 1: Participants will come to Kimball Tower on South Campus three times for approximately 1 hour each session.

Aim 2: Participants with stroke will be asked to come to Kimball Tower a total of 4 times (2 pre-tests and 2 post-tests) and participate in a 10 week in-home technology guided exercise program. Pre and post testing will be done in the two weeks pre and post the exercise program. The caregiver feedback measures would obtain information from caregivers in one session lasting 5-30 minutes depending on the amount of feedback the caregiver provides. We could conduct the interview over the phone on or near the last day of the testing session or the caregiver can do it in person during the participant's 3rd or 4th testing sessions.

10.3 Describe the estimated duration for the investigators to complete this study (i.e. all data is collected and all analyses have been completed).

Response:

It is anticipated that data collection and analyses will be completed in 2-2.5 years.

11.0 Setting

11.1 Describe all facilities/sites where you will be conducting research procedures. Include a description of the security and privacy of the facilities (e.g. locked facility, limited access, privacy barriers). Facility, department, and type of room are relevant. Do not abbreviate facility names.

NOTE: Examples of acceptable response may be: "A classroom setting in the Department of Psychology equipped with a computer with relevant survey administration software," "The angiogram suite at Buffalo General Medical Center, a fully accredited tertiary care institution within New York State with badge access," or, "Community Center meeting hall."

Response: Data collection will be done on the South Campus of UB in Kimball Tower. The building is handicap accessible and is open to the public during normal working hours. Parking spaces are reserved for participants and in addition handicapped parking is available next to Kimball Tower. The lab is located on the fifth floor of Kimball Tower. The de-identified data from the in-home exercise program will be collected through the smartphone. De-identified data will be uploaded to Amazon Simple Storage Service (Amazon S3). Security measures have been taken so that only members of the research team are able to access de-identified data on Amazon S3. If internet is not available to upload the data, data will remain stored on the phone.

11.2 For research conducted outside of UB and its affiliates, describe:

- *Site-specific regulations or customs affecting the research*
- *Local scientific and ethical review structure*

NOTE: This question is referring to UB affiliated research taking place outside UB, i.e. research conducted in the community, school-based research, international research, etc. It is not referring to multi-site research. UB affiliated institutions include Kaleida Health, ECMC, and Roswell Park Cancer Institute.

Response:

N/A: This study is not conducted outside of UB or its affiliates.

12.0 Community-Based Participatory Research

12.1 Describe involvement of the community in the design and conduct of the research.

NOTE: Community-Based Participatory Research (CBPR) is a collaborative approach to research that equitably involves all partners in the research process and recognizes the unique strengths that each brings. CBPR begins with a research topic of importance to the community, has the aim of combining knowledge with action and achieving social change to improve health outcomes and eliminate health disparities.

Response:

N/A: This study does not utilize CBPR.

12.2 Describe the composition and involvement of a community advisory board.

Response:

N/A: This study does not have a community advisory board.

13.0 Resources and Qualifications

13.1 *Describe the qualifications (e.g., education, training, experience, expertise, or certifications) of the Principal Investigator and staff to perform the research. When applicable describe their knowledge of the local study sites, culture, and society. Provide enough information to convince the IRB that you have qualified staff for the proposed research.*

NOTE: If you specify a person by name, a change to that person will require prior approval by the IRB. If you specify a person by role (e.g., coordinator, research assistant, co-investigator, or pharmacist), a change to that person will not usually require prior approval by the IRB, provided that the person meets the qualifications described to fulfill their roles.

Response:

The PI has completed a PhD program, post-doctoral training and has a productive research lab. Key personnel have completed a PhD or advanced graduate degrees in their respective fields and are involved in ongoing scholarship. All research personnel have completed CITI training. Research assistants have been trained in the lab on use of equipment, clinical assessments, and pen and paper assessments. Training includes reading pertinent literature, hands on training and training with more senior research personnel. Research assistants working with participants have completed CPR and First Aid training. Research assistants are responsible for screening potential participants, obtaining verbal consent, collecting data, managing data sets and writing. The PI will regularly communicate with research personnel regarding recruitment, data collection, data management and writing.

Describe other resources available to conduct the research.

13.2 *Describe the time and effort that the Principal Investigator and research staff will devote to conducting and completing the research.*

NOTE: Examples include the percentage of Full Time Equivalents (FTE), hours per week. The question will elicit whether there are appropriate resources to conduct the research.

Response: Key personnel with academic appointments will devote .5-.9 academic months and up to .75 summer months. Personnel with 12 month appointments will devote .3 calendar months. In addition, Graduate (9 month appointment yr 1 and 12 month appointment yr 2) and undergraduate research assistants (total of 30 hours per week) will work on the project.

13.3 *Describe the availability of medical or psychological resources that subjects might need as a result of anticipated consequences of the human research, if applicable.*

NOTE: One example includes: on-call availability of a counselor or psychologist for a study that screens subjects for depression.

Response: If individuals demonstrate they are at higher risk for falls based upon the clinical assessments, they will be encouraged to consult with their physician and given basic information regarding fall prevention strategies. If a fall were to occur during assessments or training, there are not medical resources on site. If needed, medical resources would need to be called.

13.4 Describe your process to ensure that all persons assisting with the research are adequately informed about the protocol, the research procedures, and their duties and functions.

Response: Research personnel working with the participants are trained in the use of clinical assessments, equipment used in the study and are familiarized with the research protocol. This is done through hands on training, reading pertinent literature and working with senior research personnel. In addition, all research personnel have completed CITI training.

14.0 Other Approvals

14.1 Describe any approvals that will be obtained prior to commencing the research (e.g., school, external site, funding agency, laboratory, radiation safety, or biosafety).

Response:

Prior to dispersing advertisements through Meals on Wheels, the Program of All-Inclusive Care for the Elderly (PACE), stroke support groups, senior centers, or clinical facilities, permission will be obtained from the organization to do so.

N/A: This study does not require any other approvals.

15.0 Provisions to Protect the Privacy Interests of Subjects

15.1 Describe how you will protect subjects' privacy interests during the course of this research.

NOTE: Privacy refers to an individual's right to control access to him or herself. Privacy applies to the person. Confidentiality refers to how data collected about individuals for the research will be protected by the researcher from release. Confidentiality applies to the data.

Examples of appropriate responses include: "participant only meets with a study coordinator in a classroom setting where no one can overhear", or "the participant is reminded that they are free to refuse to answer any questions that they do not feel comfortable answering."

Response:

Participants will self-select to respond to one of the advertisements for the study. They need to choose to contact the researchers to participate in the study. The settings for the phone conversation will be in private areas. The subjects will be seen in private lab areas for clinical assessment.

15.2 Indicate how the research team is permitted to access any sources of information about the subjects.

*NOTE: Examples of appropriate responses include: school permission for review of records, consent of the subject, HIPAA waiver. This question **does apply** to records reviews.*

Response: Participants will directly provide personal data to research personnel. Research personnel do not have access to medical or other records for the participant.

16.0 Data Management and Analysis

16.1 Describe the data analysis plan, including any statistical procedures. This section applies to both quantitative and qualitative analysis.

Response:

Aim 1:

Validation of smartphone with motion monitor system. We will look at consistency of motor performance across time.

Aim 2:

A strength of the proposed single-subject study design is the internal validity gained by using repeated measurement from the same individuals and the ability to replicate the effect of the intervention across participants. As is typical with single-subject designs, visual inspection will be used as the first stage of analysis to determine the general stability of performance during the baseline phase and the trend of performance change during the training intervention. Statistical analysis to corroborate the visual analysis will include time-series analysis to infer changes in trend and level across phases.⁸⁰ The serial dependency in the data for each participant will be accounted for using the autoregressive integrated moving average (ARIMA).⁸⁰ If a significant positive trend in overall performance during the training intervention is observed, the hypothesis will be accepted. To validate the effect of the training program on the performance measures, the effect on the standardized assessments will be tested. A repeated measures analysis of variance (ANOVA) will be used to assess whether there is a difference within each participant for performance on the Wolf

Motor and 9 hole peg test assessments at the start of baseline, end of baseline, start of follow-up, and end of follow-up. Post hoc pairwise comparisons will be used to assess the differences $\Delta B = B_{end} - B_{start}$, $\Delta T = F_{start} - B_{end}$, and $\Delta F = F_{end} - F_{start}$. It is hypothesized that ΔB and ΔF will be 0, indicating stable performance during the baseline and follow-up, and that $\Delta T > 0$. If these results are consistent with the findings from the functional tests, then the results will be considered valid.

16.2 If applicable, provide a power analysis.

NOTE: This may not apply to certain types of studies, including chart/records reviews, survey studies, or observational studies. This question is asked to elicit whether the investigator has an adequate sample size to achieve the study objectives and justify a conclusion.

Response:

Aim 1: In a study (N=15 young adults) we will examine the ability of the smartphone to accurately identify the above listed components for the ADLs listed in Table 1. Each participant will be asked to perform five repetitions of each activity in three different testing sessions. We will qualify the performance of our activity recognition algorithms using accuracy and area under the receiver-operator characteristic (ROC) curve (AUC). We will perform an evaluation with random hold out and cross-validation as well as leave-one-person-out evaluation. Particularly, we will compute sensitivity, specificity, and F-measure values. Then we will generate a learning curve that plots classification accuracy as a function of training set size and will add data collection time until the curve plateaus. Our previous research work has shown that it is critical to collect enough sensor training data in building robust models. Similarly, we will consider recruiting new participants until the curve plateaus.

Aim 2: Sample size estimation was based on the repeated measures ANOVA test of within subjects change in standardized assessment scores from baseline to follow-up. With $\alpha = 0.05$, power = 0.8, 4 measurements, and a desired effect size (f) = 0.25 to detect, a sample size of 15 participants is needed. This effect size is consistent with studies on functional activity performance and recovery following stroke.⁶⁸ A total of 20 participants will be recruiting to account for a 25% attrition rate.

16.3 Describe any procedures that will be used for quality control of collected data.

Validation of the system in aim 1 acts as a quality control.

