Aim 2: Examine performance changes in trained ADLs when augmenting 3D printed objects with smart technology to provide quantitative feedback on performance. Study Design: A single-subject experimental design with a multiple baseline, multiple probe testing setup is well suited to stroke rehabilitation research. With inherent variability between motor performance of individuals with stroke, there is an advantage to having participants serve as their own control. The level of stability of motor performance will be established during baseline by three different assessments (described in “Assessments” below). Each participant will have a varying length of the baseline period to establish that the intervention, rather than time, is the primary reason for any observed change in performance. For the intervention, all participants will be asked to complete a six-week in home training program as described in “Training Intervention” below. A follow-up phase, using the same assessments as in the baseline, will be repeated for the purpose of assessing carry-over post intervention. Training Intervention: Training will focus on upper extremity ADLs and manipulating or transporting the 3D printed objects instrumented with a smartphone, the smartphone will be supplied for the length of the training program (Table 1 in attached grant proposal). Participants will be cued to start their rehabilitation program by setting an alarm on the smartphone. The smartphone will be placed either in (e.g., the bowl) or on (e.g., the key) the 3D printed device. During the initial assessment, rehabilitation professionals will work with participants to determine which tasks can be completed safely. Task modifications will be made as necessary to protect joint integrity and balance. Similar to previous research in stroke, training will be tailored to the participant’s ability. The majority of training ADLs give participants the opportunity to perform them in a seated position. However, some participants may prefer to stand as this position is more functional for many of the ADLs. Participants will be asked to complete a minimum of 10 repetitions of each task they are training once a day/ five days per week for six weeks. These common ADLs include general arm movement (horizontal transport), forearm pronation and supination (pouring) and fine motor (key). Participants will receive auditory feedback on count or speed of movement in real time. Feedback will be given as described previously. The goal is to perform tasks more smoothly and in less time than the previous session. If participants have increased pain with training, they will be asked to stop doing the training tasks and contact the PI.

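### The Aim 2 acceptance sentence rests on the trend during training alone, so improvement continuing from baseline can be accepted as a training effect

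*Combined protocol and SAP*

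**What the plan says.** The Aim 2 hypothesis (section 1.2) is that completion time and normalized jerk improve with the home training. Four parts of the plan bear on how that is judged.

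- Section 3.1 gives the reason for staggering: "Each participant will have a varying length of the baseline period to establish that the intervention, rather than time, is the primary reason" for a change in performance.
- Section 9.2 introduces the performance measures thus: "We will examine the following measurements of movement and task performance for comparison between the baseline and training intervention periods".
- Section 16.1 begins with visual inspection of baseline stability and of the training trend. It then adds "time-series analysis to infer changes in trend and level across phases", with ARIMA handling serial dependency within each participant, and names as a strength of the design "the ability to replicate the effect of the intervention across participants".
- The acceptance rule follows directly: "If a significant positive trend in overall performance during the training intervention is observed, the hypothesis will be accepted". After it comes a repeated measures ANOVA on the Wolf Motor and 9-hole peg tests, which closes with "If these results are consistent with the findings from the functional tests, then the results will be considered valid".

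**The concern.** The hypothesis attributes improvement to the training, but the acceptance sentence refers to one phase and names no comparator. People repeating a task in baseline may improve through practice or familiarity. If that improvement simply carries on, the slope during training is positive and the sentence is met. The staggered baseline is the design's control for time, and as written it does not enter the stated decision.

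The rule also errs the other way. Someone who improves at once and holds the gain has a flat training phase and does not meet it.

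Two further gaps make the rule hard to apply. It does not say whether it is judged per participant or for the group. It calls for a positive trend, although improvement in both measures is a decrease.

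**Working it through.** **1. What acceptance depends on.**

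| Element of the plan | Section | Condition of acceptance? |
|---|---|---|
| Staggered baselines | 3.1 | No |
| Baseline-to-training comparison | 9.2 | No |
| Visual inspection of baseline | 16.1 | No; no stability criterion or consequence given |
| Trend and level between phases | 16.1 | No; described as corroborating the visual analysis |
| Wolf Motor / 9-hole peg check | 16.1 | No; other outcomes, placed after acceptance |
| Significant trend during training | 16.1 | Yes, the only one |

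**2. Three patterns put through the sentence.**

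- Same rate of improvement in baseline and training: the training slope is above zero, so the sentence can be met with no training effect.
- Flat baseline, then gradual gain: it can be met, correctly.
- Immediate gain, then held: the training slope is zero, so acceptance occurs only at alpha (2.5% one-sided), as with no effect.

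This result needs no numerical assumption beyond the alpha.

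**3. Is there a plan figure to reproduce?** Not for this test. The only Aim 2 sample size (section 16.2) is 15, raised to 15/(1 − 0.25) = 20 for attrition. It belongs to the ANOVA on the standardized assessments.

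**4. Illustration for one participant.** From the documents: training on 5 days a week for 6 weeks, so 30 sessions; probes on 3 days in each baseline week. Assumed: residual SD 1; drift 1 SD per 42 days in every phase; no training effect; AR(1) by calendar day of 0, 0.3 or 0.5, treated as known; one-sided 2.5%.

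With training on days 0–4 of each week, the sum of squares of time is 6 × 10 (within weeks) + 5 × 49 × 17.5 (between weeks) = 4,347.5. With independent errors:

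- SE(slope) = 1/√4347.5 = 0.01517
- Noncentrality = (1/42)/0.01517 = 1.57, on 28 df
- Acceptance probability from the noncentral t = 0.329

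Generalized least squares with AR(1) 0.3 and 0.5 gives SEs of 0.01914 and 0.02266, and acceptance of 0.224 and 0.172. At half the drift the three values are 0.115, 0.087 and 0.073.

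**5. Study level.** Binomial on 15 participants at the 1 SD rates: if 3 must pass, 49–91%; if 8 must pass, 0.2–8%. At 0.5 SD drift, 3 of 15 gives 9–24%. The documents do not say which count applies, or whether participants are pooled.

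**6. Does a cross-phase contrast remove the error?** Single series were simulated (4,000 runs each; 3 or 5 baseline weeks; autocorrelation 0 or 0.3 between successive observations; drift of 0 to 2 SD across training). A test of change in slope accepted 2–3% whatever the drift. A joint test of level and slope, at 5%, rejected in about 5%. With 3 baseline weeks and autocorrelation 0.3, the joint test detected an immediate held gain in 19% (1 SD) and 62% (2 SD). The training-only trend accepted 2–3% of those series.

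**The case against.** The strongest reply is that the acceptance sentence directly follows the description of the between-phase analysis, and no other test is named for it. A reader could take the trend to mean the change in trend from that analysis, and baseline would then count. The sentence, however, locates the trend within the training period. If a change between phases was intended, the text should say so.

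The second reply is that there are safeguards. Section 3.1 has baseline stability established by three assessments, section 16.1 starts with visual inspection, and the Wolf Motor/9-hole peg check expects no change over baseline. This stands in part: drift shared with those tests could prevent the results being called valid. But inspection has no criterion or consequence. The later check uses other outcomes and sets no margin for a change of zero. Over 1 to 5 baseline weeks the assumed drift totals only 0.10 to 0.76 SD, and a formal baseline slope test finds it in 3–14% of participants. That does not measure visual inspection, but it shows how little a short baseline reveals.

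The third reply is that the percentages are assumed and the study-level range is too wide to show how serious the problem is. This stands.

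A reader might infer that the plan has no baseline comparison. The documents do not support that: it is planned in three places and only the link to the decision is missing. A reader might also infer that slope change alone must decide. The plan analyses both trend and level, and a slope-only rule would still miss a quick, held gain.

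**Conclusion.** The point holds as a fault in the decision rule. Acceptance requires only a significant trend during training, and none of the planned comparisons with baseline is a condition of it. That follows from the text.

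The size is illustrative. Under the assumed drift of 1 SD over six weeks, 17–33% of participants with no training effect would meet the rule, and 7–12% at 0.5 SD, against a nominal 2.5%. A reader might infer that the study as a whole is likely to reach a false conclusion. The documents do not settle this: the rate is small if a majority of participants must pass and large if three suffice, and no count or pooled test is stated. That missing decision unit is a gap in detail; it should be closed in the same sentence.

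**What to change.** Replace the acceptance sentence in section 16.1 with wording such as:

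> The Aim 2 hypothesis is supported only if the planned between-phase time-series analysis shows a change from baseline to training in [trend / level / either, with the joint test or alpha split stated], towards shorter completion time and lower normalized jerk, at alpha [value], judged [in each participant, with at least k participants showing it / in one model pooled over the staggered baselines].

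The investigators choose the deciding contrast and the decision unit, and should state how tasks and the two measures combine. The stated aim of training, "The goal is to perform tasks more smoothly and in less time than the previous session", suggests gradual gain and so favours a trend contrast, but does not rule out level.

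A level change at onset needs caution. Baseline probes are two repetitions without feedback, whereas in training "Participants will be asked to complete a minimum of 10 repetitions of each task they are training", with feedback, so conditions change together with the phase. Follow-up against baseline probes, both without feedback, can support it. First the five non-training weeks need reconciling: section 9.2 puts probes in both baseline and follow-up, while section 24.0 describes all five as baseline.

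The change is to analysis wording and needs no new data. The cost is power. Under the step 4 assumptions, with 1–4 baseline weeks, slope change in one participant detects a gradual gain of 1 SD in 3–9% and of 2 SD in 3–22%. The training-only slope gives 17–33% and 53–86%, but it responds to drift in the same way. Requiring 3 of 15 participants to show slope change gives 12–19% at 2 SD, with 0.6% false acceptance. The plan states no power for this test, so no existing claim is lost. The low per-participant figures should be weighed when choosing between a replication count and pooling.
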